7 STATISTICAL PLAN

7.1 Sample Size Determination

Duration of influenza was chosen as our primary outcome because previous studies described beneficial effects of elderberry extract on this outcome (1-4) and published data is available on the elderberry extract manufactured by the company supplying elderberry extract for our study to use to calculate our sample size.(3) Forty-six total influenza positive patients randomized at a 1:1 ratio with 23 active and 23 placebo patients are needed for a power of 90% to detect a mean difference in duration of illness of at least two days with a Type I error rate of 0.05, assuming standard deviations of 1.3 and 2.5 days in the supplement and placebo groups respectively.(3) Sixty-five to one hundred patients will be enrolled in our study. We are assuming a cautious estimate of nearly a 30% dropout rate.

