3.2 Study Endpoints

Baseline data will be obtained at time of presentation including eligibility criteria, medical history, and current influenza symptoms.

Symptoms will be recorded using the scoring system described in a meta-analysis of "all published and unpublished Roche-sponsored randomized placebo-controlled, double-blind trials of oseltamivir treatment in adult influenza" (⁹). "The primary outcome will be time to alleviation of all symptoms. Seven influenza symptoms (nasal congestion, sore throat, cough, aches and pains, fatigue, headaches, and chills or sweats)" will be graded by severity as "absent" (0), "mild" (1), "moderate" (2), or "severe" (3). Alleviation will be defined to arise when all symptoms scored as absent or mild, and remain so for at least 21.5 hours." The secondary endpoints will be the time to alleviation and to complete resolution of individual and all symptoms. Patients will be followed daily until all symptoms have completely resolved and fever has remained less than 100° F for 24 hours, or for a maximum of 21 days if symptoms have not yet completely resolved for 24 hours.

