4 SUBJECT SELECTION AND WITHDRAWAL

4.1 Inclusion Criteria

Patients are eligible to be included in the study if they meet all of the following criteria:

- [1] Males or females \geq 5 years of age
- [2] With 48 hours or less of an influenza illness documented by polymerase chain reaction
- [3] Have AT LEAST 2 of the following 7 influenza symptoms (nasal congestion, sore throat, cough, aches and pains, fatigue, headaches, and chills or sweats) graded as either moderate or severe
- [4] Have been prescribed or offered a prescription of oseltamivir or baloxavir marboxil (Xofluza)

- [5] Have access to a phone
- [6] Subjects are capable of giving informed consent or have an acceptable legally authorized representative capable of giving consent on the subject's behalf with informed assent given by subject.

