7.2 Statistical Methods

Study groups will be compared on duration of illness using a two-sample unequal variance t-test; the data will be transformed (such as by log-transformation) to meet distributional assumptions, and the mean

difference between groups with 95% confidence interval will be reported. Secondary analyses will assess the time to resolution of individual symptoms, and compare study groups on adherence to protocol and side effects using two-sample t-tests and Chi-square tests as appropriate. These analyses will be performed on an intent-to-treat basis. All tests will be two-tailed and performed at a significance level of 0.05. SAS 9.4 software will be used for all analyses.

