7.3 Subject Population(s) for Analysis

All-randomized population: Any subject randomized into the study, regardless of whether they received study drug

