Grade 4 Potentially Life-Threatening is defined as "Symptoms causing inability to perform basic self-care functions OR medical of operative intervention indicated to prevent permanent impairment, persistent disability or death".

The patients will be asked to call immediately the study personnel mobile phone at [contact] for any suspected side effects at Grades 3. These patients will be referred by the principal investigator to their primary care physician, or urgent or emergency care facilities as appropriate with follow-up of their acute symptoms by the principal investigator or study coordinators until these symptoms resolve.

ATTENTION

PATIENTS WILL BE TOLD TO CALL 911 FOR ALL GRADE 4 SYMPTOMS. After their health care needs are met for Grade 4 symptoms we will ask that they please call study line for follow-up and study personnel will also keep in touch with them daily until they are well.

WRITE TIME ____AM or PM AND DATE ____OF FIRST HAVING 2 MODERATE SYMPTOMS OF INFLUENZA TIME ___AM or PM AND DATE ____FIRST DOSE OF STUDY MEDICATION GIVEN AT ENROLLMENT Guess after first dose of medication if receiving: Elderberry __OR Placebo____

CHECK TO CONFIRM PATIENTS TOLD TO KEEP ALL EMPTY AND/OR PARTIALLY FILLED STUDY MEDICATION, OSELTAMIVIR (TAMIFLU^R), OR BALOXAVIR MARBOXIL (XOFLUZA) BOTTLES FOR THE FINAL STUDY VISIT AND RETURN OF UNUSED MEDICINE IN POSTAGE PAID ENVELOPES PROVIDED AT ENROLLMENT. RECORD GUESS IF GIVEN ACTIVE OR PLACEBO MEDICATION

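### Does calling the primary variable duration of influenza or illness in 7.1 and 7.2, with no stated start time, leave the primary analysis undefined?

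*Combined protocol and SAP*

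**What the plan says.** Section 3.2 (Study Endpoints) states: "The primary outcome will be time to alleviation of all symptoms". It defines alleviation as all seven symptoms absent or mild and staying so for at least 21.5 hours. It then adds: "The secondary endpoints will be the time to alleviation and to complete resolution of individual and all symptoms". All-symptom alleviation therefore appears as both primary and secondary. No time zero is given.

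Section 7.1 (Sample Size Determination) uses another name: "Duration of influenza was chosen as our primary outcome because previous studies described beneficial effects of elderberry extract on this outcome". It sizes the trial at 23 per arm for 90% power to detect a 2-day difference, with standard deviations of 1.3 days (supplement) and 2.5 days (placebo) and a Type I error rate of 0.05.

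Section 7.2 (Statistical Methods) states: "Study groups will be compared on duration of illness using a two-sample unequal variance t-test". On symptoms, its secondary list is short: "Secondary analyses will assess the time to resolution of individual symptoms". It allows a transformation, for example to logs. Section 7.3 analyzes everyone randomized, "regardless of whether they received study drug".

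The forms hold more than one candidate time. Section 14.1 records the time of "FIRST HAVING 2 MODERATE SYMPTOMS OF INFLUENZA" and the time of the first dose. Section 14.2 records an alleviation time and, on the last day, the time at which all symptoms and fever had been resolved for 24 hours.

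**The concern.** A primary analysis needs one variable with one start and one end. Here the endpoint section and the statistical sections use different names, and nothing links them.

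- **Start.** The entry criterion in 4.1 reads "With 48 hours or less of an influenza illness documented by polymerase chain reaction". Illness in that sense begins up to 48 hours before enrollment, so a literal duration of illness would include time before randomization. The onset time needed to compute it is on the form.
- **End.** The daily form also records complete resolution. Section 7.2 lists no analysis for complete resolution of all symptoms, which could suggest that this is what duration of illness means.

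If both points were truly open, the pair of times could be chosen after the data were seen, and each choice could be defended from the text. A different end event would also be a different outcome, to which the 2-day difference and the planning standard deviations might not apply.

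**Working it through.** **1. The plan's own figure.** Inputs from 7.1 and 7.2: difference 2 days, standard deviations 1.3 and 2.5, two-sided 0.05, unequal-variance t-test, n = 23 per arm.

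- Standard error = √[(1.3² + 2.5²)/n] = √[(1.69 + 6.25)/23] = 0.588 days.
- Noncentrality = 2/0.588 = 3.40; Satterthwaite degrees of freedom = 33.1.
- Power from the noncentral t = 91.0%. At 22 per arm it is 89.7%, so 23 is the smallest number that reaches 90%.
- Enrolling 65 to retain 46 corresponds to 1 − 46/65 = 29.2% dropout, as planned.

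The total of 46 reproduces. The question is only which variable it describes.

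**2. Which end?** Compare the sections:

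| Section | Term used | Status |
|---|---|---|
| 2 | duration (and severity) of symptoms | objective |
| 3.2 | time to alleviation of all symptoms | primary, defined |
| 3.2 | time to complete resolution | secondary |
| 7.1 | duration of influenza | primary, undefined |
| 7.2 | duration of illness | tested first, undefined |

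Only one primary outcome is defined, and 7.1 calls its variable primary. Taking complete resolution as primary would contradict 3.2. The resolution time in 14.2 has other uses: it matches the rule for ending follow-up in 3.2 and 5.5, and it serves a listed secondary endpoint. The short list in 7.2 does not point the other way. It also leaves out individual-symptom alleviation, which cannot be duration of illness, so the list is simply incomplete.

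**3. Which start?** Under 5.4 and 6.2 the first dose is given before the patient leaves the hospital. The Research Schema counts the 21-day limit from enrollment. Enrollment, randomization and first dose should therefore nearly coincide for anyone dosed. The onset time in 14.1 may be there to check the 48-hour and two-moderate-symptom criteria in 4.1.

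**4. What if an analyst used onset anyway?** The lag from onset to entry is fixed before randomization, so its expected value is the same in both arms and cancels from the raw mean difference. It adds variance. The documents do not give its distribution, so the following are assumptions: lag independent of later duration, and planning standard deviations that do not already include it.

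- Uniform over 0–24 h: variance 1²/12 = 0.083 days².
- Uniform over 0–48 h: variance 2²/12 = 0.333 days². The standard deviations become √(1.69 + 0.333) = 1.42 and √(6.25 + 0.333) = 2.57.
- Extreme bound, half the patients at 0 h and half at 48 h: variance 1 day². The standard deviations become 1.64 and 2.69.

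| Lag | Power, 23 per arm | Power, 35 per arm |
|---|---|---|
| none | 91.0% | 98.5% |
| uniform 0–24 h | 90.5% | 98.3% |
| uniform 0–48 h | 88.8% | 97.7% |
| extreme bound | 84.2% | 95.8% |

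Here 35 per arm is 100 enrolled less 30%: 100 × 0.70/2 = 35. The uniform 0–48 h case costs 91.0 − 88.8 = 2.2 points at 23 per arm and 98.5 − 97.7 = 0.8 at 35. If the prior trial's standard deviations already include such a lag, the loss is zero.

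**5. Log scale.** Time added equally to both arms pulls a ratio toward 1. With lognormal durations and the planning standard deviations, adding a constant 21.5/24 = 0.896 days moves the geometric mean ratio from 0.62 to 0.68 (assumed means 3 and 5 days) or from 0.73 to 0.76 (5 and 7 days). The direction of effect is unchanged.

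**The case for a change.** The strongest case for acting is that this is the primary test and the wording would cost little to tighten. Reading duration as shorthand for 3.2 settles the end event but not the clock, and the documents nowhere state time zero. That is correct. It is also correct that under a log transformation the choice of start affects the size of the reported ratio, not only its precision.

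Larger power losses can be produced, but they do not measure this gap. Analyzing complete resolution instead of alleviation, with an assumed independent gap SD of 1 or 2 days between the two events, gives 84.2% or 65.0% at 23 per arm. That requires an endpoint that 3.2 makes secondary. Inflating both planning standard deviations by 25% gives 75.3%, but that is ordinary uncertainty about variability and would remain however the endpoint was worded.

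The alleviation prompt in 14.2 seems to ask both when alleviation occurred and when it had lasted 21.5 hours, two times 0.896 days apart. In the available text this part of the form is visibly run together, so the number of entry fields cannot be determined and no defect can be inferred. It is worth a look at the original form, no more.

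The double listing of all-symptom alleviation in 3.2 comes from a compressed sentence and changes no analysis. What stands is that the start time is unwritten.

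**Conclusion.** The concern does not call for a change to the plan. The endpoint is defined once, in 3.2, and 7.1 and 7.2 refer to it by an everyday name. The missing start is a gap that an analyst would fill with enrollment, randomization or first dose, which should nearly coincide. Choosing onset instead would leave the raw mean difference unbiased and cost about 2 points of power at 23 per arm (91.0% to 88.8%) and under 1 point at 35 (98.5% to 97.7%).

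These sizes rest on an assumed uniform 0–48 hour lag, independent of later duration and not already in the planning standard deviations. The most dispersed lag possible within 48 hours would give 84.2% at 23 per arm; a lag already included would give no loss. The judgment also rests on reading duration as the 3.2 endpoint, which the documents support but do not state.

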7.2 Statistical Methods

Study groups will be compared on duration of illness using a two-sample unequal variance t-test; the data will be transformed (such as by log-transformation) to meet distributional assumptions, and the mean

difference between groups with 95% confidence interval will be reported. Secondary analyses will assess the time to resolution of individual symptoms, and compare study groups on adherence to protocol and side effects using two-sample t-tests and Chi-square tests as appropriate. These analyses will be performed on an intent-to-treat basis. All tests will be two-tailed and performed at a significance level of 0.05. SAS 9.4 software will be used for all analyses.

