4.4.2 Data Collection and Follow-up for Withdrawn Subjects

We will continue to collect data on subjects until they are well or for 21 days if they are not entirely well only if they agree to accept our follow-up phone calls. We will call and leave messages three times before concluding a subject is truly lost to follow-up.

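### Section 7.2 gives no rule for unobserved alleviation times, so the stated analysis of all randomized patients cannot be carried out as written

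*Combined protocol and SAP*

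**What the plan says.** Section 3.2 defines the endpoint: "The primary outcome will be time to alleviation of all symptoms". Alleviation means that all seven symptoms are absent or mild and stay so for at least 21.5 hours. The same section continues contact beyond that point ("Patients will be followed daily until all symptoms have completely resolved") up to a maximum of 21 days.

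Section 4.4.2 says that data on withdrawn patients are collected "only if they agree to accept our follow-up phone calls", and adds: "We will call and leave messages three times before concluding a subject is truly lost to follow-up". Section 7.1 requires 46 patients, enrols 65 to 100, and explains the gap: "We are assuming a cautious estimate of nearly a 30% dropout rate".

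Section 7.2 states the analysis: "Study groups will be compared on duration of illness using a two-sample unequal variance t-test". The data may be transformed, for example by logarithm, and the mean difference is reported with a 95% confidence interval. It then says: "These analyses will be performed on an intent-to-treat basis". Section 7.3 names one population: "Any subject randomized into the study, regardless of whether they received study drug".

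None of these sections, nor any other part of the document, says what value an unobserved alleviation time takes, when a patient is censored, or how a patient not alleviated by day 21 is scored. No sensitivity analysis for missing outcomes is described.

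**The concern.** A t-test needs a number for every patient in it. Intent-to-treat on all randomized patients settles who is analysed, but not what number an unobserved time receives. A patient lost before alleviation either falls out of the test, which contradicts sections 7.2 and 7.3, or enters it under a rule that the plan does not contain.

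Two things are at stake. First, dropping these patients can bias the estimated difference, because long illnesses are exposed to loss for longer. Second, the primary result would rest on a handling rule that could be picked once the data are known. Section 1.1 itself criticises previous elderberry trials for having no intent-to-treat analysis, and a completers comparison would share that weakness.

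**Working it through.** **1. The plan's own figure.** Inputs from 7.1: SDs 1.3 and 2.5 days, difference 2 days, 23 per arm, error rate 0.05 (two-sided per 7.2).
- Standard error = √((1.3² + 2.5²)/23) = √(7.94/23) = 0.588.
- Noncentrality = 2/0.588 = 3.40. Satterthwaite df = 33.1.
- Welch power = 91.0% at 23 per arm and 89.7% at 22. The stated 90% with 46 patients is reproduced.
- Dropout: 1 − 46/65 = 29.2%, which matches the stated rate. The sizing thus counts 46 of 65 patients as contributing a duration and 19 as contributing none.

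**2. Why completers can mislead.** Suppose loss has a constant daily hazard h. A patient with duration T is then observed with probability exp(−hT). For a gamma duration with mean μ and SD σ, write θ = σ²/μ and k = μ²/σ². Ignoring the day-21 cap:
- share observed = (1 + hθ)^(−k)
- completers mean = μ/(1 + hθ)

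Example with an assumed placebo mean of 7 days (not in the documents), active mean 5, and h = 0.059:
- Active: θ = 1.69/5 = 0.338, k = 14.79, observed 0.747, completers mean 5/1.0199 = 4.90.
- Placebo: θ = 6.25/7 = 0.893, k = 7.84, observed 0.669, completers mean 7/1.0527 = 6.65.
- Overall observed (33 active, 32 placebo) = (33 × 0.747 + 32 × 0.669)/65 = 0.708, so loss is 29.2%.
- Completers difference = 6.65 − 4.90 = 1.75 days, against a true 2.00.

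The same formula shows when there is no bias. If loss is unrelated to T, the weights are constant. If the arms are identical with one hazard, both means shrink equally.

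**3. Simulation over a range.** Assumptions: 33 and 32 randomized, lognormal or gamma durations, placebo mean 5-10 days, plan SDs, true difference 2.0 days, constant hazard, day-21 cap.

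| Loss before alleviation | Completers estimate | Completers power | Log-rank power |
|---|---|---|---|
| 29% (ceiling) | about 1.6-1.8 d | 84-90% raw scale, 77-91% log scale | about 95-97% |
| 15% | about 1.8-1.9 d | not tabulated | not tabulated |

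At 29% loss, the restricted mean difference to day 21 is 2.00-2.05 days, with interval coverage of 93-94%. Under loss unrelated to duration, the completers estimate is 2.00-2.01 days. With identical arms and a common hazard, it is 0.00-0.01 days with 4.7-5.0% rejection.

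**4. How much the choice of rule matters.** Compare two rules on the same simulated trials: completers only, and last contact taken as the duration. On the raw scale they disagree on significance in about 15-49% of trials at 29% loss, and in 5-28% at 15% loss.

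**5. What censoring does not cure.** Take identical arms. In the active arm only, loss is 43% above the median duration and 15% below it; in placebo it is a flat 29%. The t-test shows a spurious 0.35-0.40 days and rejects in 7.6-8.4% of trials. The log-rank test rejects in 6.6-7.3%. The day-21 restricted mean is off by 0.16-0.28 days.

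**The case against.** Dropout is not the same as a lost outcome. Calls continue past alleviation to complete resolution (3.2), and missed calls are repeated (5.5, 6.2). Withdrawn patients are still followed (8.7, and 4.4.2 if they agree). The daily questionnaire also accepts a recalled alleviation time. Section 7.1 calls its rate cautious and does not define dropout. This stands, so 29% lost before alleviation is a ceiling.

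A reader might infer that the plan has chosen a completers analysis. It has not: 7.2 and 7.3 say the opposite, and inflating 46 to 65 is sample-size convention. Dropping patients is only what the test does by default when no rule is given.

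A reader might also infer that the gap more than doubles the 5% error. That needs a third rule, which gives day 21 to every lost patient, plus picking the best of three rules afterwards. Nothing in the plan suggests that scoring, since 21 days is only a follow-up limit. With three rules, at least one is significant in 12-13% of identical-arm trials at 29% loss. Without the day-21 rule this falls to 7-9%, and each rule taken alone stays close to nominal.

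The bias under a constant hazard is toward no effect, and with 50 per arm completers power is 97-99% on the raw scale. This also stands. It limits the damage but supplies no rule.

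Finally, a stated missing-data rule within the t-test framework would close the formal gap. That is fair. The log-rank test is preferred because it uses the partial follow-up of lost patients and keeps more power.

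**Conclusion.** The concern holds in this form: the handling of unobserved alleviation times is unspecified, and the stated analysis of all randomized patients cannot be carried out until it is specified. This follows from the text alone.

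The size rests on assumptions that the documents do not give: the placebo mean, the shape of the distribution and the loss mechanism. Under those used here, a true 2-day benefit is understated by about 0.2-0.4 days at the 29% ceiling and by about 0.1-0.2 days at 15% loss. Power at the ceiling falls below that of a log-rank test on the same patients.

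The documents do not show that bias will occur, nor that it would favour the supplement. Loss unrelated to duration, or identical arms with a common loss hazard, gives none.

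The unstated time origin is a related but minor gap. The enrollment form records both symptom onset and first dose. If onset precedes first dose by 0-48 hours uniformly (assumed), using onset as the origin moves the 7.1 power from 91.0% to 88.8%.

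**What to change.** In 7.2, before unblinding:
- **Deciding test:** time to alleviation in all randomized patients, by a log-rank test stratified by the randomization age groups (5-12, 13 and above).
- **Censoring:** at last contact or day 21. Keep the observed times of withdrawn patients who are still followed.
- **Effect estimate:** Kaplan-Meier curves and the restricted mean difference in days with 95% confidence interval, to a horizon fixed in advance. This keeps the days scale of 7.1.
- **Origin:** one only. Use enrollment, taken as the recorded first-dose time, or the enrollment visit for a patient never dosed.
- **Sensitivity analysis:** because censoring removes informative-loss bias only in part, lengthen the remaining illness of censored active-arm patients in fixed steps until the conclusion changes. Report loss by arm.
- **Section 7.1:** restate power for the log-rank test. For 90% power, the hazard ratio is exp(2 × (1.960 + 1.282)/√events), which is 2.60 at 46 events and 2.17 at 70.

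The outcome times and daily contacts are already collected, and the methods are standard in SAS 9.4. The costs are slightly more analysis work, a deciding test that compares hazards rather than mean days, and a log-rank test that is slightly liberal at this size (about 5-6% rejection with identical arms).

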3.3 Primary Safety Endpoints

The conditions or symptoms that will be recorded from day of presentation until influenza symptoms are resolved include; dry mouth, bad taste, nausea, vomiting diarrhea, constipation, abdominal pain,, rash, difficulty breathing, decreased drinking, dizziness and any other symptoms not previously recorded under study endpoints as outlined above. Patient symptoms and severity of illness will be monitored daily using the Division of AIDS Table for Grading the Severity of Adult and Pediatric Adverse Events ("DAIDS AE GRADING TABLE). See appendix one for all case report forms. Study patients will be asked to call for any worsening influenza symptoms or new conditions or symptoms reaching Grade 3 or 4. See also section 8 safety and adverse events.

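### Side effects, named as primary safety endpoints, are compared only by tests at 0.05; at this size a non-significant result says little about an uncommon side effect, and no interval is planned.

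*Combined protocol and SAP*

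**What the plan says.** Section 3.3, headed as the primary safety endpoints, lists eleven named conditions (dry mouth, bad taste, nausea, vomiting, diarrhea, constipation, abdominal pain, rash, difficulty breathing, decreased drinking, dizziness) plus any others. It introduces them with "The conditions or symptoms that will be recorded from day of presentation until influenza symptoms are resolved include".

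Section 7.2 is the whole plan for comparing them between arms. It will "compare study groups on adherence to protocol and side effects using two-sample t-tests and Chi-square tests as appropriate", as a secondary analysis. "These analyses will be performed on an intent-to-treat basis", and "All tests will be two-tailed and performed at a significance level of 0.05". An interval appears once, for duration of illness: the mean "difference between groups with 95% confidence interval will be reported".

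Section 7.3 defines a single analysis population: "Any subject randomized into the study, regardless of whether they received study drug".

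Section 7.1 sizes the trial on duration only. It sets 23 evaluable subjects in each arm, the number "needed for a power of 90% to detect a mean difference in duration of illness of at least two days". It then enrolls 65 to 100 patients, allowing for nearly 30% dropout. No background rate, power or precision is given for any side effect. Sections 7.2 and 7.3 do not say how patients without post-dose side-effect data are handled.

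**The concern.** A test answers only whether the arms differ at 0.05. In a trial of 65 to 100 patients, that answer will usually be no for an uncommon side effect, even when the true rate on the supplement is several times the rate on placebo. The useful question for safety is how large an excess the data still allow, and 7.2 plans no quantity that answers it.

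The denominator is a second gap. After the first day, side effects are collected by telephone (sections 5.5, 6.3 and 8.2). If patients who were never reached stay in an all-randomized denominator as if they had no events, the rates in both arms are understated. The plan neither adopts nor excludes this.

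At stake is the interpretation of the named safety endpoints. The primary efficacy result is not affected.

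**Working it through.** **Inputs from the documents.** Two-sided alpha 0.05 (7.2). Allocation 1:1, 23 per arm evaluable, 65 to 100 enrolled, dropout nearly 30% (7.1). Enrolled size per arm: 65/2 = 32.5, taken as 33, up to 100/2 = 50.

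**Assumptions.** The documents give no planning rate for side effects. Section 1.5 reports very few in earlier elderberry studies, so low placebo rates are plausible. A common-symptom case is added because influenza itself can cause several of the listed items.

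**1. The plan's own figure.** Unequal-variance t-test, difference 2 days, SDs 1.3 and 2.5 (7.1), noncentral t:
- SE at 23 per arm = √(1.3²/23 + 2.5²/23) = 0.588; 2/0.588 = 3.40; power 91.0%. At 22 per arm, power is 89.7%.
- 46/(1 − 0.29) = 64.8, so 65.

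The stated 23 per arm and 65 enrolled reproduce. They concern duration only.

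**2. Power of the side-effect comparison.** Pearson chi-square without continuity correction. Power is the sum, over all pairs of event counts with chi-square above 3.84, of the product of the two binomial probabilities.

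| Assumed rates, placebo v supplement | 33 per arm | 50 per arm |
|---|---|---|
| 5% v 15% | 29% | 39% |
| 5% v 20% | 49% | 66% |
| 10% v 25% | 37% | 53% |
| 20% v 40% | 44% | 60% |
| 20% v 60% | 94% | 99% |

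A three- to fourfold excess over a 5% background is therefore missed 34% to 71% of the time. A threefold excess over a 20% background is nearly always found.

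**3. What an interval would add.** Take 7/33 on supplement and 2/33 on placebo.
- Chi-square = 66 × (7×31 − 2×26)² / (33 × 33 × 9 × 57) = 3.22, p = 0.07.
- Risk difference = 0.212 − 0.061 = 0.152.
- Wilson limits: 0.107 to 0.378 and 0.017 to 0.196.
- Newcombe lower limit = 0.152 − √[(0.212 − 0.107)² + (0.196 − 0.061)²] = −0.02.
- Newcombe upper limit = 0.152 + √[(0.378 − 0.212)² + (0.061 − 0.017)²] = +0.32.

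Under 7.2 this result is simply not significant. The interval shows that an excess of up to 32 points has not been excluded.

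**4. The denominator, if lost patients were counted as event-free.** With 30% of each arm contributing no events, 20% becomes 0.7 × 20% = 14% and 5% becomes 0.7 × 5% = 3.5%. The difference shrinks from 15 to 10.5 points.

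The effect on power is a separate matter. With those rates it is 35% at 33 per arm and 47% at 50. If the lost patients are left out instead, 5% versus 20% has power 35% at 23 per arm (33 less 30%) and 52% at 35 per arm (50 less 30%). Most of the loss of power therefore comes from missing data. The choice of denominator mainly affects the size of the reported rates.

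**The case against.** A reader might go further than the documents allow in four ways.

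- **That the plan treats a non-significant result as proof of safety.** No section says how such a result will be interpreted. The fair criticism is that the plan offers nothing else to interpret.
- **That the plan codes lost patients as event-free.** Sections 7.2 and 7.3 give no rule. Other sections limit the problem: the first dose is given on site (5.4), side effects are asked about at each daily contact (8.2), withdrawn patients who accept calls are still followed (4.4.2), and those withdrawn under 8.7 for Grade 4 side effects, intolerance or allergy are followed until acute symptoms resolve. Losing all side-effect data on 30% of each arm is a worst case.
- **That the all-randomized population causes the low power.** Small numbers do. With the first dose given on site, treated and randomized patients should be nearly the same.
- **That eleven tests carry a 43% chance of a false positive.** The figure 1 − 0.95^11 = 43% needs eleven independent tests, each of full 5% size. Symptoms such as nausea and vomiting plausibly move together, and 7.2 does not commit to one test per item. At a 2% rate in both arms the exact size is 0.4% at 33 per arm and 1.3% at 50, so eleven independent tests give about 5% and 13%. At a 5% rate they give 31% and 39%.

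It can also be said that section 8 provides safety oversight through graded daily questions, reporting of serious events and their regular review, and that an interval adds no power. Both are true. But section 8 yields no comparison between arms, and the interval is needed precisely because power is low: it shows what remains possible.

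**Conclusion.** The point holds as a weakness of analysis and reporting. Tests at 0.05 are the only planned between-arm analysis of endpoints that the protocol itself calls primary for safety, and no interval accompanies them. For uncommon side effects, power is roughly 30% to 65% against a 2.5- to fourfold excess at the enrolled size, so a non-significant result carries little information. This rests on assumed placebo rates of 5% to 10%. At 20%, a threefold excess would almost always be detected, though a doubling would not.

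The denominator point is conditional. It matters only if patients without post-dose data are counted as event-free, and on that the plan is silent.

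The change is worth making because it is a better summary at almost no cost. It does not bear on the validity of the efficacy analysis.

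**What to change.** In section 7.2, make estimation the main safety summary:

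- For each side effect named in section 3.3, report the count in each arm and the risk difference with a 95% confidence interval (Newcombe or exact).
- Use as denominator the patients with at least one dose and at least one post-dose contact, add this set to section 7.3, and show the number without contact by arm.
- State that p>0.05 for a side effect is not evidence of no difference. If the tests are kept, present them as supplementary.

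The cost is a short change of wording and one table, with no new data and no more patients. The intervals will be wide, and statements about safety will have to be more modest. The proposed denominator does not recover lost data: a patient reached once and then lost still counts only for what was reported, which is why the contact numbers should stand beside the rates.
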